#### **4.5.3.2. Vital Signs**

The following vital signs measurements will be measured in a supine position after 5 minutes rest at baseline and each assessed visit.

- Systolic and Diastolic blood pressure
- Pulse rate

Descriptive statistics (n, mean, standard deviation (SD), median, minimum value (min), and maximum value (max)) will be presented at baseline, absolute value of vital signs parameters at each assessed visit for on-treatment period for Safety analysis set.

As per protocol SOA Section 1.3, safety vital signs data are not collected for follow up visit, therefore on-treatment period will be same as overall period.

Participants listing for all vital signs data will be produced for each treatment and period in Safety analysis set.

#### 4.5.3.3. ECG

The arithmetic mean of the three recorded 12-lead ECGs measurements will be presented in all data summaries of 12-lead ECGs measurements at predose and single measurement of post dose for days 1, 4, 7 and 10 and discharge. ECG measurements will be recorded, including heart rate (HR), PR interval, QRS duration, QT interval, and RR interval. QT intervals will be based on Fridericia's formula and reported as per captured in eCRF:

Descriptive statistics (n, mean, standard deviation (SD), median, minimum value (min), and maximum value (max)) will be presented at baseline, and absolute and change from baseline for HR, QTc and other ECG parameters at each assessed visit for on-treatment period for Safety analysis set.

As per protocol SOA Section 1.3, safety ECG data are not collected for follow up visit, therefore on-treatment period will be same as overall period.

Participants listings will be provided for all 12 lead ECGs values and findings including abnormal ECGs for each treatment sequence and period in Safety analysis set.

[figure not shown]
### 4.6. Other Analyses

No other analysis will be performed for the study.

CCI

CCI

### 4.8. Changes to Protocol Defined Analyses

CCI

## 5. SAMPLE SIZE DETERMINATION

Up to 60 healthy participants will be enrolled to either Cohort 1 (200 µg) or Cohort 2 (800 µg) to achieve at least 56 participants in the PK analysis set.

For each cohort, 30 healthy participants will be randomly assigned to a cohort to ensure at least 28 participants are included in the PK analysis set with 15 randomized to each treatment sequence.

The target number of participants in each cohort is chosen to achieve half width (refer [Table 7](#)) of the 90% CI, in the estimate of the geometric mean ratios for the primary endpoints (AUC (0-30 min.), AUC (0-inf) and Cmax).

[figure not shown]
In the previously conducted 219430 pilot PK study, there was considerable interest in AUC (0-30 min) due to larger than expected observed differences between test and reference product, in addition to observing potentially higher amounts of intra-subject variability that would classify the product as highly variable (~30%). Though, less variability was observed among AUC (0-inf) and Cmax. Due to uncertainty of what the true CVWR may be for both the reference and test products, this current study therefore has considered a more conservative assumption accounting for up to 50% intra subject variability (CVWR) in PK parameters, with a particular interest in AUC (0-30 min).

Therefore, a sample size 28 in each cohort, assuming intra subject variability (CVWR) of 50% in AUC (0-30 min.), the half width of the upper bound of the 90% CI for observed GMR (T/R) is 16.44% (refer [Table 7](#)).

For example, if the geometric ratio between test and reference is 1.06 for n=28 and CVWR = 50%, then the upper bound of the 90% CI for observed treatment ratio is  $1.06*(1+0.1644) = 1.23$  and the lower bound is  $1.06/(1+0.1644) = 0.91$  (refer [Table 8](#)).

**Table 7      Sample sizes with varying intra subject variability and associated half-widths of the 90% CI of the observed treatment ratio**

CCI

CCI

**Table 8      Sensitivity Table**

CCI

## 6. SUPPORTING DOCUMENTATION

### 6.1. Appendix 1 Study Population Analyses

The study population analyses will be based on the FAS or Enrolled participants, unless otherwise specified. A summary of the number of participants in each of the participant level analysis set will be provided.

Study population analyses will be included in analyses of participant disposition, protocol deviations, demographic and baseline characteristics, prior and concomitant medications etc. based on GSK Core Data Standards. Study population analyses will be performed for each Cohort 1 and Cohort 2 separately.

#### 6.1.1. Participant Disposition

Participant disposition will be tabulated by each treatment sequence, each period (with primary reason for withdrawal including washout period) for all participants combined with the counts and percentages of participants who complete the study, prematurely withdraw, and the reason for study withdrawal for Enrolled participants. Participants disposition will also be summarized for FAS if the difference finds between Enrolled and FAS participants.

Summary of treatment status and reasons for discontinuation of study treatment will be produced for study treatment, with the number of participants who completed study

treatment, or prematurely discontinued treatment, and the primary reasons for treatment discontinuation tabulated for the FAS.

Participant listing of the reasons for study withdrawal will be provided for each treatment sequence and period in enrolled participants.

Summary of screen failure and its reason as per eCRF will be provided for overall (Total) screened participants.

Table will be generated for summarizing the number of participants in each analysis set for all participants who provided informed consent. Listing of participants excluded from any analysis set will also be produced for Enrolled participants. Listing of planned and actual treatment will also be generated.

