### 3. ANALYSIS SETS

Analysis Set	Definition / Criteria	Analyses Evaluated
Screened	
 
• All participants who were screened for eligibility.
 
	
 
• All Screened Reason for Screen Failures
 

Enrolled	
 
• All participants who screen passed and entered in the study (who were randomized or received treatment or underwent a post-screening study procedure)
 
• Note screening failures (who never passed screening even if rescreened) and participants screened but never enrolled into the study (met eligibility but not needed) are excluded from the enrolled analysis set as they did not enter the study
 
	
 
• Study Population
 

FAS	
 
• All randomized participants who received at least a single dose period of study intervention
 
• Data will be reported according to the randomized study intervention.
 
• Single dose = 2 puffs/actuations for Cohort 1
 
• Single dose = 8 puffs/actuations for Cohort 2
 
	
 
• Study Population
 
• Exploratory PD objective
 

Safety	
 
• All participants who received at least one puff/actuation of study intervention.
 
• Data will be reported according to the actual study intervention.
 
	
 
• Estimand for secondary safety objective
 

Pharmacokinetic (PK)	
 
• All participants in the FAS who had at least 1 non-missing PK assessment (NQ values will be considered as non-missing values).
 
• Data will be reported according to the actual study intervention.
 
	
 
• Estimand for primary and secondary objective of PK parameters
 

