### Estimands for Safety

#### Cohort 1:

Test: Salbutamol HFA-152a MDI 200 μg

Reference: Salbutamol HFA-134a MDI 200 μg

The clinical question of interest for the safety secondary objective in Cohort 1 is -

What is the safety and tolerability profile of single doses 200 μg of salbutamol in Cohort 1 healthy participants delivered via MDIs?

The secondary safety estimand for Cohort 1 is described by the following attributes:

- The population is healthy male or female participants aged 18 to 55 years.
- The secondary safety endpoints are:
  - Incidence of AEs and SAEs
  - Absolute values for 12-lead ECGs recording of HR and QTc intervals at each assessed visit
  - Change from baseline for postdose 12-lead ECGs recording of HR and QTc intervals at each assessed visit
  - Absolute values of clinical laboratory parameters at each assessed visit
  - Absolute values of vital signs (systolic and diastolic blood pressure and pulse rate) at each assessed visit.
- Treatment condition is administration of salbutamol as a single 200 μg dose, given as 2 actuations each separated by a 20-second interval, each delivering 100 μg of salbutamol (as salbutamol sulfate) as the ex-valve dose for the HFA-152a MDI or HFA-134a MDI.
- The ICEs and estimand strategies are as follows:

- Study treatment discontinuation due to any reason (treatment policy strategy). Interest lies in the group of participants irrespective of whether they completed the study intervention.
- Occurrence of emesis or coughing on dosing (treatment policy strategy).
- Dosing error: Considered less than or more than prescribed dose (treatment policy strategy).
- Use of prohibited or rescue medication which impacts the PK parameters (Treatment policy strategy).
- The population level summaries to be estimated are:
  - Number and percentages for incidence of AEs and SAEs
  - Mean of absolute values for 12-lead ECGs recording of HR and QTc intervals at each assessed visit
  - Mean of change from baseline values for postdose 12-lead ECGs recording of HR and QTc intervals at each assessed visit
  - Mean of absolute of clinical laboratory parameters including vital signs (systolic and diastolic blood pressure and pulse rate) at each assessed visit

Cohort 2:

Test: Salbutamol HFA-152a MDI 800  $\mu$ g

Reference: Salbutamol HFA-134a MDI 800  $\mu$ g

The clinical question of interest for the safety secondary objective in Cohort 2 is -

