### **6.1.3. Protocol Deviations**

Important protocol deviations will be summarized using FAS. Listing of important protocol deviation will also be generated for each treatment and period in FAS.

A summary of inclusion and exclusion criteria will be produced for FAS in overall (Total) participants.

Listing for participants with inclusion/exclusion criteria deviations will be generated for each treatment sequence in FAS.

Protocol deviations will be tracked by the study team throughout the conduct of the study. These protocol deviations will be reviewed to identify those considered as important as follows:

- Data will be reviewed prior to freezing the database to ensure all important deviations (where possible without knowing the study treatment details) are captured and categorized in the protocol deviations dataset.
- This dataset will be the basis for the summaries of important protocol deviations.

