#### **6.1.4. Prior and Concomitant Medications**

Prior and Concomitant medications will be coded using WHO Drug dictionary version on or after Global B3 Sept 2023.

The counts and percentages of participants reporting each concomitant medication will be presented by study treatment sequence for FAS.

A medication will be summarized in each study period (pre/on/post) in which it was taken, so a concomitant medication that was started in the screening and stopped during active treatment will appear in both the pre-treatment and the on-treatment tables.

Concomitant medications include any medication that was taken at some point during the on-treatment period as defined in Section 6.9 of the protocol.

Participants listing of concomitant medication will also be generated for FAS.

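### Treatment status with discontinuation reasons, important deviations and concomitant medication are reported on the FAS, so anyone who stops for good part-way through the first dose is missing from all three

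*SAP*

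**What the plan says.** SAP section 3 defines the FAS as "All randomized participants who received at least a single dose period of study intervention" and then fixes what a dose is: "Single dose = 2 puffs/actuations for Cohort 1" and "Single dose = 8 puffs/actuations for Cohort 2". The Safety set is wider: "All participants who received at least one puff/actuation of study intervention".

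Three study-population displays use the FAS:

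- SAP 6.1.1 summarises treatment status as numbers completed or "prematurely discontinued treatment, and the primary reasons for treatment discontinuation tabulated for the FAS".
- SAP 6.1.3: "Important protocol deviations will be summarized using FAS". The listing of important deviations is also on the FAS.
- SAP 6.1.4: "The counts and percentages of participants reporting each concomitant medication will be presented by study treatment sequence for FAS". The medication listing is on the FAS too.

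Other displays use wider sets. Study disposition with withdrawal reasons (6.1.1) and demographics (6.1.2) are on the Enrolled set, with a repeat on the FAS if the two sets differ. Safety analyses are on the Safety set (4.5).

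Protocol 9.2 gives the Enrolled set the study-population displays and the FAS only the exploratory PD objective. Its FAS definition does not state puff counts. Both the puff counts and the FAS's study-population role are first stated in the SAP.

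**The concern.** Protocol 7.1 treats as discontinued anyone who has not had every planned dose, and it requires the primary reason in the eCRF. Someone who stops for good during the first dose meets that definition. Yet the only table of treatment discontinuation by reason is built on a set that excludes this person, and excludes them because they stopped so early.

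The plan itself foresees incomplete dosing. Coughing or emesis on dosing and receipt of less than the prescribed dose are named intercurrent events, in both the primary and the safety estimands.

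What is at stake is the completeness and internal agreement of the descriptive tables. The treatment-status table can show no discontinuations while the AE tables show one. A medicine given to this participant would appear in neither the concomitant-medication summary nor its listing.

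**Working it through.** The plan states no figure to reproduce. The check applies the set definitions to each possible puff count and then traces where the participant is reported.

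**Step 1. Set membership for a randomized participant with no dosing after Period 1** (SAP section 3)

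| Puffs in Period 1 | Enrolled | Safety | FAS |
|---|---|---|---|
| Cohort 1: 0 | yes | no | no |
| Cohort 1: 1 | yes | yes | **no** |
| Cohort 1: 2 | yes | yes | yes |
| Cohort 2: 0 | yes | no | no |
| Cohort 2: 1 to 7 | yes | yes | **no** |
| Cohort 2: 8 | yes | yes | yes |

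A participant with a partial first dose who later takes one full dose enters the FAS. The gap therefore applies only to a permanent stop.

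**Step 2. Treatment stop versus study withdrawal.** Protocol 7.1 separates the two. A participant who stops treatment should, where possible, continue other study procedures. Such a person may have no study-withdrawal reason to report.

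**Step 3. Where the reason for a stop during the first dose is summarised**

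| Type of stop | Treatment-status table (FAS) | AEs leading to discontinuation or withdrawal (Safety, SAP 4.5 and 4.5.2) | Study disposition (Enrolled, SAP 6.1.1) |
|---|---|---|---|
| AE, leaves study | absent | shown | shown, with withdrawal reason |
| AE, stays in study | absent | shown | no withdrawal to show |
| Not AE, leaves study | absent | not applicable | shown, with withdrawal reason |
| Not AE, stays in study | absent | not applicable | no withdrawal to show |

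Only in the last row is the reason missing from every summary table. In the first two rows the reason is reported, but the AE table counts one and the treatment-status table counts none.

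SAP 4.3.1.1 also promises counts of intercurrent events, which include treatment discontinuation for any reason. It names no analysis set for them. If they are made on the Safety set, the stop is counted without its reason. If they are made on the PK set, which sits inside the FAS, the person is missing again.

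Two listings show the person: participants excluded from any analysis set (Enrolled, SAP 6.1.1) and dose administration (Safety, SAP 4.5.1).

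**Step 4. Size in one cohort.** The inputs are 30 randomized per cohort (SAP section 5) and, for illustration, k participants who stop for good during the first dose while all others complete.

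- FAS table: 0/(30 − k). Enrolled or Safety table: k/30.
- k = 1: 0/29 = 0% against 1/30 = 3.3%.
- k = 2: 0/28 = 0% against 2/30 = 6.7%.

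**The case against.** The strongest reply is that nothing inferential depends on these tables. The safety estimand says "Interest lies in the group of participants irrespective of whether they completed the study intervention", and a reader might infer that the FAS tables breach it. They do not. That estimand's endpoints are AEs and SAEs, ECG, clinical laboratory values and vital signs, all analysed on the Safety set. Treatment status and discontinuation reason are not endpoints, and the PK comparison does not use these tables. This part of the reply stands in full.

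A reader might also infer that such a participant disappears from the report. The AE tables, the Enrolled disposition table and the two listings show otherwise. What survives is narrower: the missing reason in the last row of Step 3, and the possible disagreement between the treatment-status and AE counts. The listings let a careful reader explain that disagreement, but they do not tabulate reasons.

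On frequency, the documents point to a low risk. Participants are healthy, are trained with a placebo inhaler before each dosing day's dose, and are dosed under supervision. Dosing spans about 20 seconds in Cohort 1 and 7 × 20 = 140 seconds in Cohort 2. No rate is given. One could assume a per-participant probability p of 1%, 2% or 5% and compute 1 − (1 − p)^30 = 26%, 45% or 79% for at least one omission in a cohort. Those values reflect only the assumed p, and they cover any permanent stop during the first dose, not just the case where the reason is lost. They are not evidence that an omission is likely.

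Finally, a partial dose reaches the deviation table only if study-team review classes it as important (SAP 6.1.3), so its omission there is conditional.

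**Conclusion.** The gap is real and limited. As written, a participant who permanently stops after 1 puff (Cohort 1) or 1 to 7 puffs (Cohort 2) of the first dose is left out of treatment status with reasons, important deviations and concomitant medication. For one such person the treatment-status table reads 0/29 rather than 1/30.

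The reason for stopping is lost from all summary tables only for a non-AE stop by someone who remains in the study. Concomitant medication is the least covered of the three, because both its summary and its listing are on the FAS.

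This rests on reading the SAP's puff counts as the minimum for FAS entry, which is their plain meaning. It does not depend on any assumed rate. No PK or safety endpoint is affected. The correction is worth making because it is nearly free and the SAP already handles the same situation for study disposition and demographics.

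**What to change.** In SAP 6.1.1, 6.1.3 and 6.1.4, put treatment status with discontinuation reasons, important deviations and concomitant medication, including the associated listings, on the Enrolled set. This agrees with protocol 9.2. Show any participant who was never dosed on a separate line of the treatment-status table, so that they are not mixed with those who started and stopped.

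Two alternatives also close the gap:

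- Use the Safety set for treatment status and on-treatment medication, which matches the AE tables. Keep important deviations on Enrolled, because the Safety set would omit deviations in randomized participants who were never dosed.
- Extend the SAP's existing rule, under which disposition and demographics are shown on both sets when Enrolled and FAS differ, to these three displays.

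Keep the FAS for the exploratory PD analysis. The cost is SAP wording and a different population flag on planned outputs, plus duplicate tables under the second alternative if the sets differ. No extra data are needed.

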### **6.1.2. Demographic and Baseline Characteristics**

Demographic characteristics and baseline characteristics such as age, age group, sex, race, ethnicity, childbearing potential, height, weight, and body mass index (BMI) will be summarized and tabulated by treatment sequence and overall (Total) using participants in Enrolled participants. Demographic characteristics and baseline will also be summarized for FAS if the difference finds between Enrolled and FAS participants.

Listing for demographic characteristics will be produced in FAS for each treatment sequence.

Descriptive statistics will be presented for age, height, weight, and BMI. Counts and percentages will be presented for age group ( $\geq 18$  -  $\leq 55$  years), sex, race, ethnicity, childbearing potential.

### **6.1.3. Protocol Deviations**

Important protocol deviations will be summarized using FAS. Listing of important protocol deviation will also be generated for each treatment and period in FAS.

A summary of inclusion and exclusion criteria will be produced for FAS in overall (Total) participants.

Listing for participants with inclusion/exclusion criteria deviations will be generated for each treatment sequence in FAS.

Protocol deviations will be tracked by the study team throughout the conduct of the study. These protocol deviations will be reviewed to identify those considered as important as follows:

- Data will be reviewed prior to freezing the database to ensure all important deviations (where possible without knowing the study treatment details) are captured and categorized in the protocol deviations dataset.
- This dataset will be the basis for the summaries of important protocol deviations.

#### **6.1.4. Prior and Concomitant Medications**

Prior and Concomitant medications will be coded using WHO Drug dictionary version on or after Global B3 Sept 2023.

The counts and percentages of participants reporting each concomitant medication will be presented by study treatment sequence for FAS.

A medication will be summarized in each study period (pre/on/post) in which it was taken, so a concomitant medication that was started in the screening and stopped during active treatment will appear in both the pre-treatment and the on-treatment tables.

Concomitant medications include any medication that was taken at some point during the on-treatment period as defined in Section 6.9 of the protocol.

Participants listing of concomitant medication will also be generated for FAS.

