4. STUDY DESIGN

4.1. Overall design

This is a randomized, open-label, single dose, 2-sequence, 2-treatment arm, 4-way cross-over (2x2x4) single-center study in healthy participants aged 18 to 55 years. Salbutamol will be administered as either a 200 µg or 800 µg dose, given as 2 or 8 actuations respectively at 20 second intervals, each delivering 100 µg as the ex-valve dose of HFA-152a or HFA-134a. Sequential enrollment approach will be followed for the study. Participants in Cohort 2 will be enrolled once participants in Cohort 1 have completed the study. An interim analysis is planned for when last participant enrolled for the 200 µg (Cohort 1) completes their last visit, and final analysis will be conducted when the last participant of 800 µg (Cohort 2) completes their last visit.

The study has planned to enroll a total of 60 participants to either Cohort 1 (200 µg) or Cohort 2 (800 µg) to ensure at least 56 participants in the PK analysis set (see Section 9 on analysis sets). For each cohort, 30 healthy participants will be randomly assigned to a cohort to ensure at least 28 participants are included in the PK analysis set with 15 randomized to each treatment sequence.

Following treatment sequences will be applied in each cohort:

Treatment Sequence 1: TRRT

Treatment Sequence 2: RTTR

Where T is salbutamol HFA-152a (test) and R is salbutamol HFA-134a (reference).

In Cohort 1, salbutamol will be administered as single 200 µg dose, given as 2 actuations each separated by a 20-second interval, each delivering 100 µg of salbutamol (as salbutamol sulfate) as the ex-valve dose for the HFA-152a MDI or HFA-134a MDI.

In Cohort 2, salbutamol will be administered as single 800 µg dose, given as 8 actuations each separated by a 20-second interval, each delivering 100 µg of salbutamol (as salbutamol sulfate) as the ex-valve dose for the HFA-152a MDI or HFA-134a MDI.

Participants will attend a screening visit between Day-28 and Day-1. The intervention period will be 10 days with dosing on Day 1, Day 4, Day 7, and Day 10. Participants will be discharged on Day 11. There will be a follow-up period between Day 12 and Day 18.

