6.9. Prior and concomitant therapy

Participants must abstain from taking prescription medications from 30 days prior to admission until completion of the follow-up visit or early discontinuation. An exception is made for hormonal contraceptives, which may be used throughout the study.

Participants must abstain from taking nonprescription drugs (including vitamins, recreational drugs, and dietary or herbal supplements) from 14 days prior to admission until completion of the follow-up visit or early discontinuation.

Vaccination is not allowed from 2 weeks prior to admission until discharge.

Paracetamol/Acetaminophen, at doses of ≤ 2 grams/day, is permitted for use any time during the study, except during the 24 hours predose or postdose. The reason that acetaminophen is not permitted during the 24 hours predose or postdose is because acetaminophen may decrease the excretion rate of salbutamol, which could result in a higher serum level (<https://go.drugbank.com/drugs/DB01001>). Other concomitant medications may be considered on a case-by-case basis by the investigator in consultation with the medical monitor.

Other medication to treat AEs may only be prescribed if deemed necessary by the investigator. If medication is used, the name of the drug, the dose, and dosage regimen will be recorded in the eCRF.

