### Primary estimand: -

#### **Cohort 1:**

Test: Salbutamol HFA-152a MDI 200 µg

Reference: Salbutamol HFA-134a MDI 200 µg

The primary clinical question of interest for Cohort 1 is -

What is the GMR for Cohort 1 in primary PK parameters (AUC(0-30min), AUC(0-∞) and Cmax) of salbutamol HFA-152a and salbutamol HFA-134a in healthy participants after administration of single dose of 200 µg?

The primary estimand for Cohort 1 is described by the following attributes:

- The population is healthy male or female participants aged 18 to 55 years.
- The primary PK parameters endpoints are AUC(0-30min), AUC (0-∞) and Cmax.
- Treatment condition is administration of salbutamol as a single 200 μg dose, given as 2 actuations each separated by a 20-second interval, each delivering 100 μg of salbutamol (as salbutamol sulfate) as the ex-valve dose for the HFA-152a MDI or HFA-134a MDI.
- The ICEs and estimand strategies are as follows:
  - Study treatment discontinuation due to any reason (hypothetical strategy).
  - Occurrence of emesis or coughing on dosing (hypothetical strategy).
  - Dosing error: Considered less than or more than prescribed dose (hypothetical strategy).
  - Use of prohibited or rescue medication which impacts PK parameters (hypothetical strategy).

For all ICEs, interest lies in evaluating the primary PK parameters and comparisons of the ratio of 2 formulations for each of the primary PK parameters in a hypothetical scenario in which the participant had not experienced an intercurrent event. This is to minimize potential confounding of ICEs on individual PK parameters across treatment periods.

- The population level summary to be estimated is:

Ratio of adjusted GM (for logarithmic transformed values) of 2 formulations (test/reference) with 90% CI for each primary PK endpoint.

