## 4.5. Safety Analyses

Safety analysis set will be used for the analysis of safety endpoints. Secondary safety estimand to analyses safety endpoints (refer Section 4.3.1.1.) will be implemented for Cohort 1 and Cohort 2. Safety analysis will be summarized by study treatment.

Details of the planned displays for safety data are provided in Output programming specifications (OPS) and will be based on GSK Data Standards and statistical principles.

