#### **6.2.2. Study Period**

Assessments and events will be classified within each cohort according to the time of occurrence relative to the study treatment period (days).

**Pre-Treatment:** For the presentation of serious adverse events (SAEs), concomitant medications, and other assessments in pre-treatment is defined as -

Date of assessment < Study treatment start date of period 1 (day 1).

**On-Treatment:** For the presentation of adverse events (AEs), serious adverse events (SAEs), concomitant medications, 12-lead ECG, vital signs, and other assessments in on-treatment is defined as -

Study treatment start date of period 1 (day 1) <= Date of assessment <= Study treatment stop date of period 4 (Day 10) or early withdrawal + 1 day

Worsening in AE (change in AE severity from lower severity to higher severity category) relative to the pre-study treatment state will also be considered as on-treatment AE.

If time of assessment or study treatment is not collected (missed), the following assessment on the first dose date will be assumed to be taken prior to the first dose and therefore considered pre-treatment.

As per study design, Four Treatment Periods of the study are defined below.

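### On-treatment concomitant medication is summarised only by treatment sequence, so the table cannot attribute its use to the test or the reference inhaler

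*SAP*

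**What the plan says.** SAP 6.1.4 sets the columns of the concomitant medication table: "The counts and percentages of participants reporting each concomitant medication will be presented by study treatment sequence for FAS". It then gives the split in time: "A medication will be summarized in each study period (pre/on/post) in which it was taken". A participant listing is also planned, but its layout by treatment or period is not stated.

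SAP 6.2.2 defines on-treatment as one interval: "Study treatment start date of period 1 (day 1) <= Date of assessment <= Study treatment stop date of period 4 (Day 10". One day is added to that upper limit, and the limit comes earlier for a participant who withdraws. Protocol 4.1 gives the two sequences: "Treatment Sequence 1: TRRT" and "Treatment Sequence 2: RTTR".

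Elsewhere the SAP works by product. Section 4.5 states: "Safety analysis will be summarized by study treatment". Section 4.5.2 assigns each adverse event to the period of the dose it follows. Section 6.2.2 already defines the treatment periods, with Periods 1 to 3 running from one dose to the next and Period 4 ending one day after its dose.

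The plan also treats some medication as relevant to salbutamol exposure. Protocol 6.9 restricts acetaminophen around dosing because "acetaminophen may decrease the excretion rate of salbutamol, which could result in a higher serum level". The primary estimand in SAP 1.1 includes this intercurrent event: "Use of prohibited or rescue medication which impacts PK parameters (hypothetical strategy").

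**The concern.** Sequence is a sensible column for anything fixed before dosing, such as demographics or medical history. Medication taken after dosing can be a response to the product just inhaled, and Protocol 6.9 allows medication for adverse events when the investigator judges it necessary. In this design every participant who completes dosing receives both products twice, so a sequence column mixes them in equal parts. An adverse event will appear under the product that preceded it, while the medicine given for it will appear under a column that names no product.

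At stake is a supporting piece of the tolerability comparison: whether medicines were needed more often after one inhaler than after the other.

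**Working it through.** The plan states no figure on this point, so there is none to reproduce. The check follows from the design.

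**Inputs from the documents**
- Test (T) and reference (R) doses per completed sequence: TRRT 2 and 2; RTTR 2 and 2 (Protocol 4.1).
- Participants: 30 per cohort, 15 per sequence (Protocol 1.1 and 4.1).
- One on-treatment window covering all four doses (SAP 6.2.2).

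**Assumptions, not in the documents**
- A medicine is taken after a T dose with probability pT and after an R dose with probability pR, independently between doses.
- All four doses are received and there is no period effect.

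**Formulas for at least one use**
- Either sequence: 1 − (1 − pT)² × (1 − pR)². The expression is the same for TRRT and RTTR, so the expected difference is zero for any pT and pR. Exchanging pT and pR leaves it unchanged.
- By product: 1 − (1 − pT)² for T and 1 − (1 − pR)² for R.

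**Use after both products, pT = 20% and pR = 5%**
- By product: 30 × (1 − 0.80²) = 10.8 for T; 30 × (1 − 0.95²) = 2.9 for R.
- By sequence: 15 × (1 − 0.80² × 0.95²) = 15 × 0.4224 = 6.3 in each column.

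**Use after T only (pR = 0), over a range of pT**

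| pT | TRRT, of 15 | RTTR, of 15 | T, of 30 | R, of 30 | SD of sequence difference |
|---|---|---|---|---|---|
| 5% | 1.46 (9.75%) | 1.46 | 2.9 | 0 | 10.8 points |
| 10% | 2.85 (19%) | 2.85 | 5.7 | 0 | 14.3 points |
| 20% | 5.4 (36%) | 5.4 | 10.8 | 0 | 17.5 points |
| 30% | 7.65 (51%) | 7.65 | 15.3 | 0 | 18.3 points |

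The last column is √(2P(1 − P)/15) in percentage points, where P is the expected proportion in a sequence. If use follows R only, the two sequence columns are identical to those shown and the two product columns change places. The planned table therefore cannot separate opposite situations.

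**When the balance fails.** Participants who stop after one period have had 1 T dose in TRRT and 0 in RTTR; after three periods, 1 and 2. At pT = 20% and pR = 0 the expected proportions are then 20% against 0%, and 20% against 36%. T also falls in Periods 1 and 4 of one sequence and Periods 2 and 3 of the other, so a period effect could separate the columns. In each case the columns move, but the table still does not assign use to a product.

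**The case against.** The strongest reply is that this is a layout choice with little riding on it. The table belongs to the study population appendix, not to Safety Analyses, so the rule in SAP 4.5 does not govern it. No endpoint, interval or decision uses it. Adverse events are already attributed to dosing periods and summarised by product, with severity, relatedness and discontinuation, and the severity grades in Protocol 10.3.4.2 refer to the need for intervention. Participants are healthy and confined, most medication is barred, and Protocol 4.3 reports adverse events in low numbers in previous studies. With 30 per cohort, attribution by hand from a listing is feasible. All of this stands, and it limits the point to a minor one.

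A reader might infer that the PK ratio is exposed. The documents do not support that. Medication affecting PK is an intercurrent event, SAP 4.2.2 sets the affected data in that period to missing, and SAP 4.3.1.1 plans counts of these events. Acetaminophen inside the restricted window would be a protocol deviation, and SAP 6.1.3 lists important deviations by treatment and period.

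These provisions do not supply the missing summary. The intercurrent event counts cover only prohibited or rescue medication that affects PK, with no product breakdown stated. The deviation output by treatment and period is a listing restricted to deviations judged important. Permitted medication given for an adverse event falls under neither.

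**Conclusion.** The point holds as a low-severity, cheap improvement. The on-treatment table cannot attribute medication use to a product, whatever the rates. With complete dosing and no period effect the expected sequence difference is exactly zero.

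A reader might go further and expect the two columns to agree in the results. That does not follow: with 15 per sequence, chance differences with an SD of roughly 11 to 18 percentage points are to be expected over the range shown. They carry no product information.

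The counts above illustrate the mechanism and do not forecast use, because the documents give no medication rates and actual use may be low. The practical loss is confined mainly to medicines given for adverse events and to permitted medicines, as part of tolerability by product. The primary PK analysis is largely unaffected.

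**What to change.** In SAP 6.1.4:

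- Keep sequence columns for pre-treatment medication.
- Add, or switch to, an on-treatment summary by product. Assign medication started after a dose to that dosing period, using the attribution rule in SAP 4.5.2 and the periods in SAP 6.2.2.
- Show medication taken in the 24 hours before a dose, including acetaminophen, on its own line against the product of the upcoming dose. The SAP periods alone would place it under the preceding product, which differs from the upcoming one at the change from Period 1 to 2 and from Period 3 to 4 in both sequences.
- Flag medication given for an adverse event.

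The cost is SAP wording and a changed column variable. Medication must already be dated to be placed before, during or after treatment, so no new visit or sample is needed. The 24-hour line may need clock times for medication taken on the day before a dose; the documents do not say whether these are recorded, so a convention for missing times should be stated. One small drawback is that continuing medication such as hormonal contraceptives, or any medicine spanning periods, counts under both products and needs a footnote.
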